# 1. Amendment History

Amendment No.	Protocol Version No.	Date	Author(s) of changes	Details of Changes made
1. Minor	3.0	18/11/14	[name] and [name]	
 
Points of clarification requested by Trial Steering Committee:
 
Additional information to clarify inclusion/exclusion criteria
 
Move 3 month post-op long leg x-ray to 1 year time point
 
Add clarification statement regarding mechanical axis targets from surgery
 
Clarify version of AKSS score being used
 
Correct omission of FJS score in text.
 
Ack by REC 22.12.15 Ack by R&D 05.01.15
 

2. Substantia	1 3.2	05/12/16	[name] [name]	Additional routes to approach patients added Approved by REC -07.12.16 Not approved by R&D- to be include in next sub amendment and approved by MHRA prior to R&D approval
3. Substantia	4.0 I	11.10.17	[name] [name] [name]	
 
Addition of human performance laboratory analysis at 2 year follow- up
 
Update of 12.3.2. Reporting of SAEs, SADEs, UADEs to the sponsor
 
Update of patient recruitment target and
 

				recruitment phase extension. Sections 19, 21 and 23. Flowchart and Gantt Chart updated.
				4. Inclusion of participant and nurse questionnaires at 2 or 5 year follow up
				5. Inclusion of newsletter at 4 and 7 years follow up to maintain participant engagement
				Submitted to REC Submitted, with previous amendment to MHRA
4. Minor	4.2	03/03/2021	[name] [name]	Update research team to replace [name] with [name]

# Approvals for Amendment number 3 (Substantial) were approved as follows:

- 1. REC Approved by West of Scotland REC 4 on 14 MAR 2018
- 2. MHRA Approved by MHRA on 03 APR 2018
- 3. Sponsor Approved by NHS Greater Glasgow & Clyde on 14 APR 2018

# Rationale for sample size amendment

On re-visiting the power calculation, it appears that the original calculation had included a conservative LTFU rate of ~23%. At the time of compiling the Study Recovery Plan (March 2017) the study statistician looked at the available data we had obtained. Our actual LTFU was 8%. Re-doing the power calculation based on a realistic LTFU of 10% meant that we could reduce the target number to 80 whilst still retaining 90% power for the primary outcome measure to ensure that the most robust and complete dataset possible is obtained to reliably answer the research question, and detect a clinically significant difference between the 2 treatment arms. The Study Recovery Plan was approved by NIHR EME on 03 MAY 2017.

EME Project: 12/12/12Protocol vs 4.2 3rd March 2021

# 2. Synopsis

Study Title	Explanatory comparative study of conventional Total Knee Arthroplasty versus Robotic assisted Bi-UniCompartmental Knee Arthroplasty
Type of study	Pre- CE marking / extension of current CE marking
Trial Design	Randomised Controlled Trial
Trial Participants	Patients with osteoarthritis of the knee affecting both the medial and lateral compartments
Planned Sample Size	80
Follow-up duration	10 years
Planned Trial Period	15 years
Primary Objective	To carry out an explanatory randomised controlled trial to compare a novel robotic assisted surgical technique (Bi-Unicompartmental Knee Arthroplasty) against a standard surgical technique (Total Knee Arthroplasty) in patients with osteoarthritis of both the medial and latera compartments of the knee.
Secondary Objectives	
 
To provide evidence of early phase efficacy and safety for Robotic Assisted Bi-Unicompartmental Knee replacement.
 
To determine the biomechanical mechanism through which patients derive benefit from Robotic Assisted Bi-Unicompartmental Knee replacement.
 

Primary Endpoint	Percentage of patients with a bi-phasic (normal) moment curve during gait (level walking)
Secondary Endpoints	
 
Percentage of patients with a bi-phasic (normal) moment curve during gait (level walking) at two years
 
Biomechanical performance–Gait during stair climb/descent and lunge, functional activity assessment (using electrogoniometers).
 
Activity – Overall daily activity levels, maximum sport/physical activity, functional activity test times (stair climb, timed up and go)
 
Impairment - Range of motion, proprioception, quadriceps strength (short term outcome) and progression of OA in contralateral knee (long term outcome).
 
Clinical Outcomes – Clinical knee scores (Oxford Knee Score, New American Knee Society Score and Forgotten Joint Score), pain, analgesic use, complications, implant fixation and satisfaction.
 
Safety profile (Determined by revision rate, adverse events, robotic system errors and accuracy of implantation)
 
Accuracy of surgical implantation (determined by post-op CT analysis)
 
MAKO Restoris MCK
 

Manufacturer Name	MAKO Surgical Corp (Florida, USA)
Principle intended use	Unicompartmental Knee Replacement (CE Marked)
Study use	Bi-Unicompartmental Knee Replacement (not currently CE marked for this indication)

# 3. Abbreviations

ACL AKSS Bi-UCKA	Anterior Cruiciate Ligament American Knee Society Score Bi-UniCompartmental Knee Arthroplasty
FJS	Forgotten Joint Score
CRF	Case Report Form
OA	Osteoarthritis
OKS	Oxford Knee Score
PCL	Posterior Cruiciate Ligament
RIO	Robotic arm Interactive Orthopaedic
ТКА	Total Knee Arthroplasty
UKA	Uni-Compartmental Knee Arthroplasty
VAS	Visual Analogue Scale

### 4. Background: Existing research and Rational

Osteoarthritis (OA) is the most common form of joint disease. It causes pain and stiffness and affects at least 8 million people in the UK imposing a considerable economic and personal burden. The knee is one of the most common sites affected by OA. Felson et al surveyed 1,800 subjects aged 63-94 and reported radiographic evidence of knee OA in 27% of subjects under the age of 70 and 44% over the age of 80, indicating a high prevalence of this disease in the knee joint (1).

The knee can be divided into three anatomical compartments; medial, lateral and patello-femoral (figure 1). OA can develop in any one of three compartments in isolation, or, more commonly in two or more compartments. Knee Replacement, or Arthroplasty, is the current surgical treatment of choice for end stage OA of the knee. In England and Wales 76,870 Knee Replacements were carried out in 2010 which represents an increase of 30% since 2005 (2). There were a further 6884 Knee

Replacements carried out in Scotland(3). In the UK and worldwide there are 3 main forms of Primary Knee Arthroplasty utilised; Total Knee Arthroplasty (91%),

Medial or Lateral Unicompartmental Knee Arthroplasty (8%) and Patello-femoral Arthroplasty (1%) (2). Total Knee Arthroplasty (TKA) is the most commonly used Arthroplasty for end stage OA and is necessary for patients with OA of all three compartments of the knee. However, it is also frequently used in patients with less extensive Bi or UniCompartmental disease.

TKA is highly successful in reducing knee pain and revision rates for TKR are relatively low at just under 3%, 5 years after surgery (3). Despite this there remains a significant number of individuals who are either dissatisfied with their outcome or who continue to suffer chronic pain associated with their knee joint. Estimates of the number of dissatisfied patients range form 9-19% (4-8), while chronic pain occurs in 13-30% of patients (9-10). Revision surgery is generally only carried out where the knee joint is either infected or the implant has loosened, as few patients with chronic post-operative knee pain are offered revision surgery, revision as an endpoint is a poor indicator of successful surgery. There are many potential reasons for the high rate of dissatisfaction in this patient group including poor replication of normal knee kinematics by current TKA prosthesis.

Knee kinematics in TKA patients have been consistently shown to be worse than aged matched controls (11-13). Poor knee kinematics are likely to be perceptible by patients and therefore influence satisfaction with surgery and ability to confidently undertake activities. High demand activities are likely to be severely limited by the poor kinematics offered by TKA designs and this is reflected in patient satisfaction surveys. Mohamed et al report 20% dissatisfaction with results of TKA surgery for improving ability to participate in recreational activity (14).

In TKA surgery the anterior cruciate ligament is removed, although the posterior cruciate ligament is sometimes retained depending on surgeon preference, prosthesis type and individual patient factors. The primary function of the anterior cruciate ligament is to resist anterior displacement of the tibia on the femur when the knee is flexed and control the screw-home mechanism of the tibia in terminal extension of the knee. The main function of the posterior cruciate ligament is to allow femoral rollback in flexion and resist posterior translation of the tibia relative to the femur. The PCL also acts as a secondary restraint of external rotation of the tibia with increasing knee flexion. Removal of the ACL and PCL inevitably impacts on patients gait patterns and knee kinematics.

Unicompartmental Knee Arthroplasty (UKA) is currently used as an alternative to TKA when only one side of the knee joint is diseased; usually the medial side. In contrast to TKA, UKA involves a minimally invasive surgical approach removing only the damaged areas of the joint.

Figure 1 Compartments of the knee

UKA involves smaller surgical incisions, less bleeding, quicker recovery, and less bone loss than TKA. Crucially, in UKA surgery neither the prosthesis nor the surgery interferes with existing knee ligaments and damage to the quadriceps tendon and muscle is usually avoided. This results in quicker post-operative recovery, lower pain, better post-operative knee kinematics(which are closer to normal than that achieved with TKA), greater knee stability and better stair-climbing ability than TKA (15-16).

Proprioception (awareness of the position of the joint) is important for balance when standing or moving and is also essential for many everyday tasks such as driving. Loss of proprioception occurs during progression of OA, but is improved in the majority of patients after UKA. Issac et al have demonstrated 60% reduction in postural sway (a marker of proprioception) after UKA compared to just 7% improvement after TKA (17). Proprioception has three components 1static awareness of joint position, 2- awareness/detection of movement, and 3- a closed loop efferent activity which starts reflex responses and regulates muscles. A key component of this system is the mechanoreceptors found in the fibers of the ACL. These receptors (along with the mechanoreceptors located in the PCL, the collateral ligaments and capsular fibers), play an important role in the complicated neural network of proprioception. Loss of knee proprioception occurs in patients with ACL injuries/deficiencies and after TKA surgery, in both cases damage or loss of the ACL mechanoreceptors are key contributors. Loss of proprioception leads to a feeling of instability and giving way even though the knee itself does not actually sublux on clinical examination. The ability to preserve proprioception or even improve it after knee arthroplasty is vital for improving outcome of knee Arthroplasty as lack of proprioception leads to altered gait and therefore non-physiological joint loading.

In a comparative gait analysis between UKA and TKA, Chassin et al have demonstrated that a greater percentage of UKA patients (70%) maintained a normal biphasic flexion/extension moment pattern about the knee when compared with similar groups of TKA patients (23%)(18-19). Other studies have found similar low proportions of patients achieving biphasic gait after TKA; Simon et al report just 20% with PCL retaining TKA and Wilson et al 25% with PCL sacrificing TKA (20-21). Gait has two phases swing (when the foot is no longer in contact with the ground) and stance (when parts of the foot are in contact with the ground). Stance phase represents 60% of the gait cycle, with normal gait requiring stability throughout the 4 phases of stance: heel strike, foot flat, heel off and toe off. Knee moment is a measure of the turning effect produced by a force about the knee axis. A bi-phasic 'normal' gait pattern occurs when the moment curve oscillates between extension and flexion during the stance phase of gait (Figure 2). Abnormal sagittal moment patterns that are not bi-phasic are described as being either, a quadriceps avoidance patterns - "stiff leg gait" - (where an extension moment is present throughout stance phase of gait), or guadriceps over use pattern (where a flexion moment is present throughout stance phase of gait). The net effect of a persistent flexion moment is to limit knee extension, which in turn causes mechanical overload of the joint during gait (walking). Development of an abnormal gait pattern following TKA may therefore have important additional consequences over time. Gait patterns are predictive of component migration and prosthetic loosening (22). Furthermore, following unilateral TKA, osteoarthritis is exacerbated in joints in the non-operated limb and this deterioration may be accelerated by biomechanical factors such as aberrant joint loading in the operated limb. Additionally, excessive pre-operative knee flexion moments are predictive of anterior knee pain post-surgery, further underlining the importance of achieving correct post-operative gait in order to produce a post-operative knee with 'normal' feel and function (23).

Although UKA offers potential functional advantages over TKA, one of the greatest challenges to both uptake of UKA by surgeons and the ultimate success of the surgery has been the technically demanding nature of the surgery. Ideal placement of the joint

[figure not shown]

Figure 2 Graph representing the biphasic knee moment pattern in the sagittal plane (solid black line), knee flexor moment pattern (dashed red line), knee extensor moment pattern (dashed blue line)

prosthesis and optimal soft tissue balancing can be difficult to reproduce accurately by hand and eye with only mechanical guides for assistance, prosthesis placement is further complicated by variable patient joint anatomy and ligament laxity. Poor prosthesis alignment has been associated with early failure of UKA and is likely to contribute to the higher revision rate observed with UKA in comparison to TKA (1.4% vs 4.6% at 3 years) (24).

In recent years advances in Orthopaedic surgery have been afforded by the introduction of surgical navigation systems which aid the surgeon in achieving accurate and repeatable implantation of devices. Most navigation systems utilise a passive optical tracking system. An infrared-emitting camera is used to monitor the position of tracking rods inserted into the patient's femur and tibia to facilitate tracking of bone position and hence the knee joint, the system also tracks surgical instruments being used.

In UKA surgery accuracy has been further advanced by the introduction of Robotic Assistive technology. There are now a limited number of Robotic systems available to facilitate UKA surgery. These are based around the principal of surgical navigation but with a robotic arm or tool used to accurately resect the necessary bone, providing accurate, reproducible implant positioning. Currently the system with the greatest market share is the MAKO Robotic arm Interactive Orthopaedic (RIO) System, which has been in use since 2006.

A pre-operative CT scan is used by the RIO system to build a 3D model of the patient's knee. This is then used by the surgeon to plan implant positioning prior to surgery with a high degree of accuracy. The system calculates which areas of bone need to be removed in order to allow correct fit of the implant.

Traditionally surgeons would use jigs and saw blades to resect bone for this type of surgery resulting in inaccurate cuts and heat generated bone necrosis. The RIO system uses a high speed, water cooled milling burr attached to a haptic robotic arm to remove bone with submillimetric accuracy, removing the minimum amount of bone required. The surgeon manipulates the arm guided by on screen CAD images of the patient's joint and haptic feedback from the robotic system (Figure 3). Milling outside of the pre-planned zones is prevented by the robotic arm. The potential advantages of the system are:

- 1. Minimal bone removal with the burr able to cut exact 3D dimensional shapes providing a perfect fit with implants
- 2. Accuracy of implant positioning is significantly improved over that achieved with conventional instruments (fig 3)
- 3. Post-operative knee alignment is improved
- 4. Decrease in immediate post-operative pain
- 5. Improved post-operative knee kinematics

[figure not shown]

Figure 3 RIO Screen shot - 3D model with bone still to be resected coded Green

The MAKO RIO system has been in use at Glasgow Royal Infirmary since 2009 and has been evaluated by the Orthopaedic Research Unit at Glasgow Royal Infirmary and the University of Strathclyde Bioengineering Unit as part of a randomised controlled trial comparing robotic assisted and traditional, medial UKA surgery (n=150).

Our early data from this study show increased accuracy of implant placement. The robotic system implanting all knees evaluated to date (100%) within 3 degrees of target for tibial flexion/extension, compared to just 38% with manual instrumentation. At 3 months post-operatively there is a 10 point difference in American Knee Society Score. However, the most impressive difference relates to post-operative pain, with those receiving robotic assisted surgery consistently reporting 50% lower pain scores from day 1 post-op to 3 months post-op (further time points are not yet available).

Currently the MAKO RIO system is used for either medial or lateral UKA, yet the system has the facility to implant both medial and lateral UKA at the same time in the same knee – Bi-UniCompartmental Knee Arthroplasty (Bi-UCKA). Bi-UCKA surgery offers the functional and kinematic benefits of UKA for a proportion of the patients with arthritis affecting the medial and lateral sides of the joint who would normally be faced with the limitations of TKA.

In order for patients to be suitable for and benefit from Bi-UCKA surgery they need to have intact Cruciate Ligaments; Douglas et al 2010 demonstrated that 78% of TKA patients have an intact ACL (34). Our own internal audit has revealed very similar rates in our cohort. Exclusions to Bi-UCKA surgery include: absence of cruciate ligaments, flexion contracture >10°, deformities with bone and soft tissue changes that make a compartmental approach to surgery unsuitable. Bi-UCKA could offer significant functional benefits for between 9,000 and 18,000 people in the UK every year who currently receiving TKA for OA of the knee. As Bi-UCKA is tissue preserving it can retain the normal biomechanical function of the knee to a much greater extent and hence may, if carried out accurately using robotic assistance, lead to a better functional and kinematic outcome than is currently achieved with TKA. Figure 4 demonstrates the differences in bone removal between Bi-UCKA and TKA. Bi-UKA surgery may also offer a valuable precursor to TKA surgery particularly for younger patients who are likely to outlive their joint replacement and require revision surgery at a later time point. Conversion from Bi-UKA to TKA in these patients may delay or prevent the need for costly and complex revision TKA surgery.

Figure 4 UKA, TKA and Bi-UCKA radiographs highlighting the difference in bone resection required.

We hypothesise that robotic assisted Bi-UCKA surgery undertaken in appropriately selected patients can offer improved knee kinematics and proprioception in comparison to that afforded by TKA. Furthermore we hypothesise that accurate positioning of implants by robotic assistive technology will improve implant survivorship in Bi-UCKA to the levels achieved with TKA and UKA.

We propose to undertake a randomised controlled trial to compare TKA and robotic assisted Bi-UCKA. We will use a battery of impairment and functional tests to explore the mechanisms underpinning any functional improvements that are observed.

# 6. Research Objectives

## Hypothesis:

The use of robotic assistive technology in Bi-UniCompartmental Knee Arthroplasty is a safe and clinically effective surgical alternative to Total Knee Arthroplasty that offers improved kinematic, clinical and functional outcome for patients with OA of the medial and lateral compartments of the knee.

### Aims:

- 1. To carry out an explanatory randomised controlled trial to compare a novel robotic assisted surgical technique (Bi-Unicompartmental Knee Arthroplasty) against a standard surgical technique (Total Knee Arthroplasty) in patients with osteoarthritis of both the medial and lateral compartments of the knee.
- 2. To provide evidence of early phase efficacy and safety for Robotic Assisted Bi-Unicompartmental Knee replacement.
- 3. To determine the biomechanical mechanism through which patients derive benefit from Robotic Assisted Bi-Unicompartmental Knee replacement.

# **Research Questions:**

- 1. What are the biomechanical kinematic benefits of Robotic Bi-UCKA surgery compared to TKA?
- 2. Are improved knee kinematics and proprioception associated with better clinical and functional outcomes after surgery?
- 3. Is the revision rate after Robotic Assisted Bi-UCKA surgery comparable with TKA surgery?
- 4. Does Robotic Assistance facilitate accurate implantation and alignment of all 4 components of a Bi-UCKA?

# 7. Research design

The study will be a prospective randomised double blinded controlled study comparing two surgical techniques. Patients randomised to Group 1 of the study (controls) will receive a standard TKA. Patients randomised to group 2 will receive Bi-UKA surgery carried out with the aid of Robotic Assistive Technology.

The study will be blinded, meaning that researchers undertaking post-operative patient assessments will not be informed which intervention patients have been randomised to receive. Surgeons involved in the study will be aware of which arm of the study patients have been randomised to. However, all post-operative data relating to the study will be collected by independent research nurses and no post-operative data will be collected by the operating surgeons. Patients will not be directly informed which arm of the study they have been randomised to.

Randomisation will be carried out after informed consent has been obtained and prior to the day of surgery. This duty will be carried out by research nurses and not by the investigators. A webbased interface will be used to access a dedicated randomisation programme created by the NIHR registered Clinical Trials Unit at the University of Aberdeen's Centre for Healthcare Randomised Trials (CHaRT) which is supporting the trial. Randomisation for the study will be stratified by surgeon.

Pre-operative and post-operative data collection will be carried out by research nurses at the time points specified in this protocol. Data will be collected on paper Case Report Forms (CRF) and this will be transcribed into a secure database. We have successfully used similar methodology for several other randomised controlled trials.

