#### 9. Planned interventions

Patients will be randomised to one of two interventions.

**Group 1- Standard TKA (Control):** Patients receiving TKA will be have a fixed bearing, cruciate sacrificing posterior stabilised Zimmer NexGen LPS TKA. These will be implanted using traditional surgical techniques and without the aid or robotics of navigation. This is the current standard of care treatment at the investigative centre and the routine method of TKA implantation in the majority of centres in the UK currently.

Mechanical axis targets for limb alignment for this group will be zero degrees.

**Group 2- Robotic assisted Bi-UKA (Experimental):** Patients randomising to Bi-UCKA will receive two unicondylar fixed bearing MAKO Restoris MCK implants, one implanted on the medial side of the knee and the other on the lateral side. These implants will be inserted with the aid of robotic assistance using the MAKO RIO Robotic System. A midline incision with medial and lateral quadriceps sparing parapatellar approaches will be used.

There are no fixed mechanical axis targets for the Bi-UCKA group. Instead the surgeon will aim to restore the constitutional angle of the joint.

All other pre and peri-operative factors will be equal for both groups. All patients will receive a spinal anaesthetic combined with peripheral nerve block and prophylactic antibiotics. Above knee tourniquets will be used routinely. Post-operative rehabilitation will consist of daily physiotherapy for the duration of the patients stay in hospital. After discharge a routine physiotherapy class will be offered for 7-14 days after surgery. Additional physiotherapy will only be offered to those patients who fail to achieve standard rehabilitation milestones and in particular those with restricted range of motion. The need for additional physiotherapy will be determined by a blinded practitioner.

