# Decreased patient impairment will be measured using:

- Knee joint proprioception
- Active and passive Range of Motion
- Isometric Quadriceps strength
- Progression of OA in the contralateral knee will be measured using Kellgren and Lawrence grading of knee X-rays

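### The double-blind label rests on not telling patients and assessors the allocation; with a robot in one arm only, under spinal anaesthesia, patient blinding is not assured for the subjective secondary outcomes

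*Protocol*

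**What the plan says.** Section 7 calls the trial a "prospective randomised double blinded controlled study comparing two surgical techniques". It supports the label with three statements:

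- On assessors: "researchers undertaking post-operative patient assessments will not be informed which intervention patients have been randomised to receive".
- On patients: "Patients will not be directly informed which arm of the study they have been randomised to".
- On surgeons, who know the allocation: "no post-operative data will be collected by the operating surgeons".

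Section 9 describes the two operations. The Bi-UCKA implants are placed with the MAKO RIO robot. The TKA implants are "implanted using traditional surgical techniques and without the aid or robotics of navigation". Anaesthesia is common to both arms: "All patients will receive a spinal anaesthetic combined with peripheral nerve block".

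Section 4 explains that most navigation systems use a camera to "monitor the position of tracking rods inserted into the" femur and tibia, and that robotic systems build on the same principle.

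On one long-term outcome, section 11.1 states: "Progression of OA in the contralateral knee will be measured using Kellgren and Lawrence grading of knee X-rays".

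**The concern.** Not telling people the allocation blinds them only if they cannot work it out. Here the arms differ in ways that a patient, or someone examining the leg, might notice, and the protocol describes nothing that hides those differences.

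This matters because many secondary outcomes depend on the patient's report (Oxford Knee Score, Forgotten Joint Score, pain, satisfaction) or on effort or the assessor (range of motion, quadriceps strength, timed tests, X-ray grade). These carry much of the claim of clinical benefit. A patient who believes that the new robotic operation was used may report or perform differently for that reason alone. A paper calling such results double-blind would credit them with a protection that the design does not assure.

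**Working it through.** The point rests on no figure, so the check is a reading of the text, one possible cue at a time.

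1. **Theatre (patient).** All patients have a spinal anaesthetic. The robot, which section 4 describes as driving a high-speed water-cooled burr, is used in the Bi-UCKA arm only. Section 17.4 promises a detailed explanation of the study before consent, so patients presumably know that one arm uses a robot. No sedation and no screening from sight or sound is described. The anaesthetic is the same in both arms and is no cue by itself; it matters because it may leave the patient aware of equipment that is not the same. Section 5 expects Bi-UCKA to take 20-30 minutes longer, but a patient has one operation and nothing to compare it with, so duration is a weak cue.

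2. **Leg (patient and assessor).** Section 4 places tracking rods in the femur and tibia for most navigation systems and ties robotic systems to that principle. Section 9 excludes navigation from the TKA arm. Separate rod scars in the Bi-UCKA arm are a probable inference, but neither section states them. Section 9 gives a midline incision for Bi-UCKA and no incision for TKA. No covering of the knee at assessment is described.

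3. **X-rays (grader).** Contralateral grading is from knee films. Table 1 lists AP and lateral knee views and long-leg views without saying whether both knees appear. On any film that shows both, the implant reveals the arm and also marks the film as post-operative. No masking is described.

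4. **CT.** Section 5 and Table 1 give CT to both arms, so CT is not a cue.

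5. **Check on unblinding.** The note to Table 1 adds a patient questionnaire on which operation participants thought they had, to study patient bias. It is completed at 2 or 5 years, whereas the primary outcome is at 1 year and patient-reported scores start at 3 months. It measures belief and does not prevent unblinding. By then the belief may also reflect how well the knee has done. The Amendment History mentions a nurse questionnaire, whose content is not given.

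6. **Primary outcome.** Section 11 classifies gait as biphasic when the maximum knee moment is positive and the minimum negative. Assessor judgement does not enter. A patient's belief could still affect how he or she walks, but nothing in the protocol suggests that it would change the sign of a moment.

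7. **Assessors.** Section 7 has research nurses randomise, and independent research nurses collect post-operative data. I take *independent* to mean that the two are different people; section 7 does not say so outright.

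Items 1 to 3 leave routes by which the allocation could be inferred, and the text closes none of them. Items 4 to 6 limit what follows from that.

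**The case against.** The protocol does more than withhold the allocation. Surgeons collect no post-operative data. The need for extra physiotherapy is decided by a blinded practitioner (section 9). Unblinded safety reports are kept from blinded staff and statisticians (section 12.2.3). The perceived-surgery questionnaire shows that patient bias was recognised. Several secondary outcomes are instrument- or event-based: two-year biphasic gait, electrogoniometry, activity monitoring, CT accuracy and revision. All of this stands, and a reader who infers that nothing was done about blinding would be wrong. None of it hides the theatre, leg or X-ray cues.

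A reader might also infer that rod wounds mark the Bi-UCKA arm for certain. Section 4 describes navigation systems in general; it does not describe this trial's wounds or say that they lie apart from the main incision.

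Nor do theatre cues unblind assessors directly: they reach an assessor only through what the patient says. Awareness in theatre is itself an assumption, because the protocol is silent on sedation.

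Timing also limits the remedy. The protocol version is dated March 2021, while section 21 ends 1-year data collection in July 2019. In Table 1, gait, proprioception, strength and timed tests stop at 2 years. Covering the knee could now help mainly with range of motion at 5 and 10 years, and it cannot blind patients.

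**Conclusion.** The concern holds in limited form. The double-blind label claims more than the protocol secures. Assessors are blinded by non-disclosure and by separation from the surgeons. Patients are not told their arm, but their blinding is not assured. Classification of the primary outcome is largely protected, so the exposure is mainly in the patient-reported and assessor-dependent secondary outcomes.

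Its size cannot be derived from the protocol. A reader might try. With 36 per arm, the standardised difference detectable with 90% power at two-sided 5% is (1.96 + 1.282) x sqrt(2/36) = 0.764. If expectation shifted a score by 0.2-0.4 SD in the 50-100% of patients who recognised their arm, the bias would be 0.1-0.4 SD, or 13-52% of that difference. But the shift and the recognition rate have no source in the protocol, and the 36 per arm was set for a binary outcome. The range should not be read as an estimate.

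The conclusion assumes that some patients are aware enough in theatre, or see enough of the leg afterwards, to infer the arm. The X-ray point assumes that some graded films show the operated knee. This is worth correcting, because the label will pass into every report through the 10-year follow-up, but it does not undermine the primary comparison.

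**What to change.** 1. In section 7, replace *double blinded* with *assessor-blinded; patients not told their allocation, patient blinding not assured*. Add that patient-reported outcomes will be interpreted as open to expectation bias, with the perceived-surgery questionnaire used to inform that interpretation.

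2. In section 11.1, require contralateral Kellgren and Lawrence progression to be graded with the operated knee cropped or masked on any film that shows it, and with films in random time order. Masking is also what makes the random order effective, since a visible implant dates the film. Existing films can be graded this way, as can those from the 5- and 10-year visits.

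3. Optionally, cover the knee identically in both arms at the remaining visits where range of motion is measured. This may need a second person at each visit, and the gain is small.

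Items 1 and 2 cost a wording change, minor image preparation and a less favourable blinding claim. They alter no treatment and no visit. Theatre cues cannot be undone, so the corrected label is the more important change.
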